1.0 Objectives

1.1 Describe the purpose, specific aims, or objectives of this research.

Response:

The purpose of this project is to develop and test affordable, effective strategies to reduce caregiver burden and associated negative effects (e.g., depression and fatigue) and to increase caregivers' satisfaction and self-efficacy, so that they can continue providing home-based care to their care recipients (CRs) who are members of the Program of All-inclusive Care for the Elderly (PACE). This project will connect PACE organizations and university occupational therapy (OT) graduate level curriculum to produce a practical, sustainable care model. In this project, a research component pertains to assess effectiveness of OT interventions

1.2 State the hypotheses to be tested, if applicable.

NOTE: A hypothesis is a specific, testable prediction about what you expect to happen in your study that corresponds with your above listed objectives.

Response:

We have three reteach questions and two hypotheses.

1. What are challenges that caregivers are facing in caring for their care recipients?
2. Which solutions were accepted and effective?
3. The intervention group will reduce caregiver burden and depression, while the control group will not.
4. The intervention group will increase the scores of positive aspect of caregiving and self-efficacy while the control group will not.
5. At 6-months after intervention, does the effect of our intervention exist?

In addition, we will identify the rate of care recipients who live in the community opposed to moving to a nursing home for both groups, and the number of falls and emerveny visits of care recipients.

Scientific Endpoints

2.1 Describe the scientific endpoint(s), the main result or occurrence under study.

*NOTE: Scientific endpoints are outcomes defined before the study begins to determine whether the objectives of the study have been met and to draw conclusions from the data. Include primary and secondary endpoints. Some example endpoints are: reduction of symptoms, improvement in quality of life, or survival. Your response should **not** be a date.*

Response:

Primary endpoint for the study is the reduction of caregiver burden and depression. Secondary endpoints is the improvement in positive aspect of caregiving and self-esteem.

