3.0 Study Design

3.1 Describe and explain the study design (e.g. case-control, cross-sectional, ethnographic, experimental, interventional, longitudinal, observational).

Response:

We will use a qualitative method to understand difficulties that caregivers are facing and to document solutions and their implementation process; and a quantitative method using a randomized contoured trial with pre-, post- and follow-up experimental design. A treatment group will receive a 1 to 2-month interventions to solve caregiving challenges, and a control group will receive usual support. Assessments will be conducted at baseline, 2 months (posttest), 4 months (follow-up), and 6 months post intervention.

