A month after initial assessment, OTGS will contact CRs for follow-up and 2 months later, the posttest will be administered. At 4 months, follow-up interview will occur. The number of home visits (4-6) will vary depending on case. Finally 6 months after the intervention, a phone call will be made, asking the same questions before and the number of falls and emergency visits of care recipients in the past 10 months. After each interview, a participant will be paid \$20. (The total maximum is \$80).

9.2 Describe what data will be collected.

NOTE: For studies with multiple data collection points or long-term follow up, consider the addition of a schedule or table in your response.

Response:

The outcome measures will use established instruments. To measure caregiver burden, 12-item Zarit Burden Interview (ZBI), for depression, 20-item Center for Epidemiology Study-Depression (CES-D) will be used. Positive Aspect of Caregiving has 9 items. Self-esteem and fatigue questions will use a visual analog scale from 1 to 10. In addition, items of activities of daily living (ADL, e.g., eating, dressing, and toileting) and instrumental ADL (IADL, e.g., meal preparation, housekeeping) that caregivers are assisting will be identified. We do not assess or provide interventions for CRs directly, but we ask caregivers about CR's cognitive levels using Global Deterioration Scale, and functional levels using FIM to assess ADL and OARS' IADL. We also ask if care recipients fell or visited an emergency room.

 *9.3 List any instruments or measurement tools used to collect data (e.g. questionnaire, interview guide, validated instrument, data collection form).*

Include copies of these documents with your submission.

Response:

The assessment form is attached.

9.4 Describe any source records that will be used to collect data about subjects (e.g. school records, electronic medical records).

Response:

We will not use other sources or records. But if the cause of cognitive impairment is not clear, we will ask the PACE to provide it for us. This is written in the consent form.

*9.5 Indicate whether or not **individual** subject results, such as results of investigational diagnostic tests, genetic tests, or incidental findings will be shared with subjects or others (e.g., the subject's primary care physician) and if so, describe how these will be shared.*

Response:

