10.0 Study Timelines

10.1 Describe the anticipated duration needed to enroll all study subjects.

Response:

The duration need to enroll all participants is 19 months.

10.2 Describe the duration of an individual subject's participation in the study. Include length of study visits, and overall study follow-up time.

Response:

Each participant intervention is 1-2 months and it will take 30 – 45 minutes for each of 4 time assessments. From the beginning of the contact to the end of 4h assessments, it will be about 10 months.

10.3 Describe the estimated duration for the investigators to complete this study (i.e. all data is collected and all analyses have been completed).

Response:

2. 5 years

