16.0 Data Management and Analysis

16.1 *Describe the data analysis plan, including any statistical procedures. This section applies to both quantitative and qualitative analysis.*

Response:

For two hypotheses, we first analyze a linear trend of dependent variables over time. If they are linear, we will use Generalized Estimating Equation to compare the two groups' slopes. A main effect and an interaction effect will be examined. If it is not, we will use Repeated Measures ANOVA with a between-factor. The contrasts within a group and the difference between groups will be performed as post hoc tests. To answer the last research question to find the difference between

the 4-months data and 6 month after intervention (or at 10 months), we will use Repaeated measurs ANVA with a between-factor.

To answer research questions, we will list all challenges for both groups and solutions for the treatment group. The effectiveness of solutions will be evaluated using a Likert Scale (from very effective to not effective at all) and percentages will be reported. For the rate of continued community, living at 4 months will be tabulated for both groups and a chi-square test will be used. The number of falls and emergency visits will be compared for these two groups using Mann Whitney U-test.

The significance level for primary analyses will be set at .05. SPSS 26.0 will be used for statistical analyses.

16.2 If applicable, provide a power analysis.

NOTE: This may not apply to certain types of studies, including chart/records reviews, survey studies, or observational studies. This question is asked to elicit whether the investigator has an adequate sample size to achieve the study objectives and justify a conclusion.

Response:

The sample size for this study was determined by a power analysis based on the study similar to our study (Kamiya et al., 2014). The effect size found in the article was $d = .65$. We will use a directional hypothesis; therefore, we set $\alpha = .05$, and in order to achieve 80% of statistical power, we will need 30 participants in each group, therefore 60 in total. Expecting 25% of attrition, we will recruit 75 participants.

16.3 Describe any procedures that will be used for quality control of collected data.

Response:

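### Continued community living is compared only at 4 months although follow-up runs to about 10 months, so later nursing-home moves are not analysed; the comparison is underpowered at either time

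*Combined protocol and SAP*

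**What the plan says.** Section 1.2 adds, after the hypotheses, that "we will identify the rate of care recipients who live in the community opposed to moving to a nursing home for both groups". It gives no time point.

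Section 16.1 supplies one. Community "living at 4 months will be tabulated for both groups and a chi-square test will be used". No other analysis of residence is planned.

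Follow-up continues after that. Section 3.1: "Assessments will be conducted at baseline, 2 months (posttest), 4 months (follow-up), and 6 months post intervention". Section 10.2: "From the beginning of the contact to the end of 4h assessments, it will be about 10 months". Section 16.1, for the last research question, compares "the 4-months data and 6 month after intervention (or at 10 months" after the start. Section 9.1 describes the last contact as a telephone call "asking the same questions before and the number of falls and emergency visits of care recipients in the past 10 months".

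Section 9.2 lists the data to be collected. It covers the caregiver scales, the care recipient's cognition and function, falls and emergency room visits. It does not name place of residence at any visit. The assessment form cited in 9.3 is an attachment that is not part of the text reviewed.

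**The concern.** The project's purpose in 1.1 is to help caregivers go on providing care at home, and the background links high burden to nursing-home placement. Residence is the outcome that speaks most directly to that purpose. The protocol also asks whether the effect persists six months after the intervention, and it looks back over 10 months for falls and emergency visits. Residence alone is tied to the earlier time point.

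Two things are at stake. A care recipient who moves between month 4 and the final call counts as living in the community in the only planned comparison. And a non-significant chi-square test resting on a handful of moves could be read as showing no effect on placement.

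**Working it through.** **The plan's own figure.** Section 16.2 uses d = 0.65, a directional alpha of .05 and 80% power. The normal approximation gives n = 2 × (1.645 + 0.842)² / 0.65² = 29.3, so 30 per group; the noncentral t gives 80.0% power at 30. The plan's figure reproduces. It is a calculation for a mean difference and does not cover residence.

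**Inputs for residence**
- Analysed number: 75 recruits less 25% attrition is 75 × 0.75 = 56.25, about 28 per arm (16.2).
- Times: month 4 (16.1) and about month 10 (10.2, 16.1). Six months after a 1-2 month intervention could also mean about month 8 (3.1, 10.2).
- Assumed, because the documents give no rate or effect: control move rates by month 4 of 5%, 10% or 15%; hazard ratio 0.3 or 0.5; constant hazard.

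**Formulas**
- Control risk at month T: 1 − (1 − p4)^(T/4). The exponent is 2 at month 8 and 2.5 at month 10.
- Treatment risk: the same, with the exponent multiplied by the hazard ratio.
- Share of control moves after month 4: 1 − p4/pT.
- Power: exact binomial enumeration of the uncorrected chi-square test, two-sided 5%, 28 per arm.

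**Share of control moves falling after month 4**

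| Control risk at month 4 | Risk at month 8 | Risk at month 10 | Share after month 4, to month 8 | Share after month 4, to month 10 |
|---|---|---|---|---|
| 5% | 9.8% | 12.0% | 49% | 59% |
| 10% | 19.0% | 23.2% | 47% | 57% |
| 15% | 27.8% | 33.4% | 46% | 55% |

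Example: 1 − 0.10/0.232 = 57%.

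**Expected moves in both arms, and power**

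| Control risk at month 4 | Hazard ratio | Moves by month 4 | Power, month 4 | Moves by month 10 | Power, month 10 |
|---|---|---|---|---|---|
| 5% | 0.3 | 1.8 | 3% | 4.4 | 20% |
| 10% | 0.3 | 3.7 | 15% | 8.6 | 38% |
| 15% | 0.3 | 5.5 | 26% | 12.6 | 51% |
| 5% | 0.5 | 2.1 | 3% | 5.1 | 12% |
| 10% | 0.5 | 4.2 | 9% | 9.9 | 18% |
| 15% | 0.5 | 6.4 | 14% | 14.5 | 25% |

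Expected moves somewhat more than double in every row. Power rises in every row and stays well below 80%.

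**Sensitivity**
- Further loss: if 22 per arm remain at month 10 (an assumption), power at a hazard ratio of 0.3 is 13/31/43% instead of 20/38/51%.
- Weaker effect: at a hazard ratio of 0.7 and 28 per arm, power goes from 2/6/8% to 7/9/11%.
- Rarer moves: with 2% of controls moving by month 4, power at month 10 is about 3% even at a hazard ratio of 0.3.
- One-sided test: 16.2 states a directional hypothesis for the sample size. A one-sided 5% version of the test at month 10 would reach at most 65% in the scenarios tabulated.
- Number needed: halving a proportion of 10% (or 20%) with 80% power, two-sided, takes about 435 (or 199) per arm.

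**The case against.** Community living is neither a primary nor a secondary endpoint. It enters as an additional outcome with no time point, so tabulating it at 4 months contradicts nothing in 1.2. That is correct, and it limits the weight of the point.

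Three stronger readings are tempting, and the documents do not support them.

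- *The 4-month cut is why the comparison has little chance of showing a difference.* The 10-month test is also underpowered in every scenario run. The main cause is a sample sized for a continuous outcome.
- *Most nursing-home moves are left out.* The documents give no move rate. The share is above one half only if the hazard is roughly constant and the last contact is at month 10. At month 8 it is just under one half.
- *Data already in hand would be discarded.* Sections 9.1 and 9.2 do not name residence at any visit. The 4-month analysis presupposes that it is collected, and the final call involves "a phone call will be made, asking the same questions before". Whether those questions include residence cannot be seen from the text.

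It can also be said that losses may grow by the last call, which would offset part of the gain. This is fair: with 22 per arm the gain is smaller, though month 10 still compares well with month 4 at 28 per arm (13/31/43% against 3/15/26% at a hazard ratio of 0.3).

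**Conclusion.** The point holds in a limited form. The only planned comparison of community living is at 4 months, follow-up continues to about 10 months, and no reason is given for treating residence differently from falls and emergency visits. Moves after month 4 go unanalysed: about half or slightly more of those during follow-up, if the hazard is constant.

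Extending the analysis would somewhat more than double the expected number of moves. It would not turn this into an adequately powered test: the best tabulated case is 51%, and that assumes a 70% reduction in hazard. All move rates and hazard ratios here are assumptions. The result should be presented as descriptive at either time point. This is a worthwhile, inexpensive improvement to an additional outcome; it does not affect the primary analysis.

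**What to change.** In 9.1 and 9.2, name place of residence as a data item, and at the final call already planned ask whether the care recipient has moved to a nursing home and on what date. State in which month that call falls, because 3.1 and 10.2 can be read as month 8 or month 10.

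In 16.1, analyse community living through the final assessment and keep 4 months as an earlier look. Report the number of moves per arm and the risk difference with a 95% confidence interval, labelled as descriptive. As an illustration of the precision to expect, risks of 23.2% and 12.3% with 28 per arm give a difference of 10.8 percentage points (from unrounded risks) with a half-width of 1.96 × √(0.232 × 0.768/28 + 0.123 × 0.877/28) = 19.8 points. The dates would also allow a time-to-move display that uses partial follow-up from participants lost before the last call.

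The cost is one added question and a few lines of text. The downside is some extra missing data at the last contact, so the number with known residence should be reported for each arm at both times.

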4.0 Local Number of Subjects

4.1 Indicate the total number of subjects that will be enrolled or records that will be reviewed locally.

Response: 60

4.2 If applicable, indicate how many subjects you expect to screen to reach your target sample (i.e. your screen failure rate).

Response: 75

4.3 Justify the feasibility of recruiting the proposed number of eligible subjects within the anticipated recruitment period. For example, how many potential subjects do you have access to? What percentage of those potential subjects do you need to recruit?

Response:

There are approximately 300 PACE enrollees/members in Eire and Niagara Counties. Among them 50% are having cognitive impairments. Of 150, we expect about 1/2 to 2/3 of them have caregivers who are experiencing challenges in caregiving; therefore 75 to 100 caregivers. The sample size for this study was determined by a power analysis based on the study similar to ours (Kamiya et al., 2014). The effect size found in the article was $d = 0.65$. We will use a directional hypothesis; therefore, we set $\alpha = .05$, and in order to achieve 80% of statistical power, we will need 30 participants in each group, therefore 60 in total. Expecting 25% attrition, we will recruit 75 participants.

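### The stated 80% power rests on a one-sided test that the analysis plan never specifies; the two-sided version of the same calculation gives about 70%

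*Combined protocol and SAP*

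**What the plan says.** The power statement appears in section 4.3 and again in section 16.2. Both take d = 0.65 from a cited study, declare "We will use a directional hypothesis", set alpha at .05 and conclude that "in order to achieve 80% of statistical power, we will need 30 participants in each group, therefore 60 in total".

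The tests are set out in section 16.1. The first choice depends on the shape of the time trend: "If they are linear, we will use Generalized Estimating Equation to compare the two groups' slopes". The alternative is: "If it is not, we will use Repeated Measures ANOVA with a between-factor". Within-group and between-group contrasts are listed only as post hoc tests. The level is given as follows: "The significance level for primary analyses will be set at .05". Section 16.1 does not mention sidedness, a one-sided contrast or a halved p-value.

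Section 1.2 states the expected direction in words: burden and depression should fall in the intervention group, and positive aspects of caregiving and self-efficacy should rise.

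**The concern.** A power figure is useful only if it describes the test that will be run. The 80% depends on putting the whole .05 in one tail, and section 16.1 contains nothing that does so. An ANOVA F test rejects for any departure, whether benefit, harm or a difference in profile. A GEE Wald test as usually reported is also two-sided. An analyst who follows 16.1 and compares the reported p-value with .05 is not running the test that was powered.

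A null result would then be read against a Type II error of 20% that was not derived for the test performed. For a two-sided comparison of two means on the same inputs, that error is about 30%.

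**Working it through.** **Inputs.** From sections 4.3 and 16.2: d = 0.65, n = 30 per group, alpha = .05, directional, 80% power. From 16.1: level .05, sidedness not stated, GEE slopes or repeated measures ANOVA. From 3.1: four assessments. Not in the documents: any within-person correlation.

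**Step 1: reproduce the stated figure.** For a two-sample t test with n per group, the noncentrality is d × √(n/2) = 0.65 × √15 = 2.517, with 2n − 2 = 58 df.
- One-sided .05: critical value 1.672, power **80.0%**. The smallest n for 80% is 30 (29 gives 78.8%). The sponsor's figure is reproduced.

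**Step 2: the same calculation, two-sided.**
- Two-sided .05: critical value 2.002, power **69.7%**. The two-group ANOVA F test with f = 0.325 gives the same value.
- The smallest n for 80% is 39 per group (38 gives 79.9%, 39 gives 80.9%).
- With 30 per group, the difference detectable with 80% power is d = 0.74.

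The 30 per group therefore comes from the one-sided assumption alone. Normal approximations tell the same story: 80.9% one-sided, 71.1% two-sided.

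**Step 3: tests closer to those in 16.1.** These need a correlation ρ, so the results are illustrations under compound symmetry with complete data on 30 per group.

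(a) Group-by-time F test with 3 and 174 df, four visits, group differences (0, 0.65, 0.65, 0.65). The mean difference is 0.4875. The sum of squares about it is 0.4875² + 3 × 0.1625² = 0.3169. The noncentrality is (n/2) × 0.3169/(1 − ρ) = 4.753/(1 − ρ).

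(b) Two-sided 1-df slope comparison, visits at 0, 2 and 4 months, group difference growing linearly to 0.65, normal approximation. With three equally spaced visits the slope is the last value minus the first, divided by 4. So z = 0.65 × √(n/2) / √(2(1 − ρ)) = √(3.169/(1 − ρ)), and power = Φ(z − 1.96).

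| ρ | (a) noncentrality | (a) power | (b) z | (b) power |
|---|---|---|---|---|
| 0.3 | 6.79 | 56.5% | 2.13 | 56.7% |
| 0.5 | 9.51 | 72.7% | 2.52 | 71.1% |
| 0.6 | 11.88 | 82.7% | 2.81 | 80.4% |
| 0.7 | 15.84 | 92.6% | 3.25 | 90.1% |

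The planned tests may fall below or above 80%, depending on a quantity that the documents do not state.

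**The case against.** The calculation in 16.2 is correct on its own inputs, so this is not an arithmetic slip. The direction is declared in advance: 4.3 and 16.2 say so, and section 1.2 gives it for each outcome. With two groups and linear time, the GEE slope comparison is one signed coefficient, and a 1-df Wald chi-square is a squared z, so a one-sided p-value could be taken from it. All of this stands. It leaves one gap: 16.1 does not say that the slope will be tested one-sided, and the multi-df ANOVA fallback cannot be.

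Three stronger readings are tempting, and the documents do not support them.
- *The trial has 70% power.* The 69.7%, like d = 0.74, belongs to a single two-group comparison of means, which 16.1 does not plan. Step 3 shows that the planned tests could do worse or better.
- *Sidedness would be chosen after seeing the data.* A one-sided test of the slope would follow a direction already in writing. The omission leaves the rule unclear, but does not show an intention to choose later.
- *A one-sided test would hide harm on the CES-D.* Sections 17.1 to 17.9 handle safety through an individual score threshold reported to the PACE. No between-group safety test is planned, so the sidedness of the efficacy test does not affect that mechanism.

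**Conclusion.** The concern holds as a mismatch between the power section and the analysis section. The 80% is a property of a one-sided .05 two-sample t test at d = 0.65 with 30 per group. Section 16.1 specifies no such test and no one-sided rule. On the sponsor's own inputs, the two-sided version loses about 10 percentage points (80.0% to 69.7%).

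This conclusion takes d = 0.65 and 30 analysable caregivers per group as given. That the tests in 16.1 would be read two-sided is an inference from the methods named there, since 16.1 does not say it. The power of the planned repeated-measures tests is undetermined. The range of about 57% to 93% rests on assumed compound symmetry, correlations of 0.3 to 0.7 and the effect patterns in Step 3.

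**What to change.** 1. In 16.1, name one primary 1-df between-group contrast, for example the group-by-time slope or the group difference in change at posttest. State its sidedness, preferably two-sided at .05.
2. In 4.3 and 16.2, state that the two-sided version of the existing calculation gives about 70% power at d = 0.65, or 80% at d = 0.74, and that this is for a single two-group comparison of means. Add the power of the named contrast over a stated range of within-person correlations, with the assumed correlation structure.
3. If the directional test is kept, 16.1 must say that this 1-df contrast is tested one-sided at .05. The multi-df ANOVA F test cannot serve that purpose.

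The cost is wording in three sections. No additional caregivers or visits are needed. The only downside is a less favourable stated power.
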